#### 6.1.4 **Treatment duration**

The planned duration of treatment is 128 weeks for individual patients. However, each patient is eligible to one voluntary treatment interruption of up to 24 weeks (approximately 6 months) after an initial treatment duration of at least 12 weeks. After such a voluntary treatment interruption within the 128 weeks of the Treatment Epoch patients may return to the treatment schedule.

Subjects can be discontinued from treatment earlier due to unacceptable adverse events and/or at the discretion of the investigator or the subject.

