#### Confidential Protocol No. CAMG334ADE03

Novartis

Clinical trial protocol V01

Page 32

Novartis	Confidential	
Clinical trial protocol V01	Protocol No. CAMG334ADE03	

	Screen					Ope	n-label	Treatm	ent Epo	och				During drug holiday	First visit after drug holiday	Follow up 
Visit number 	0	Baseline	V101	V102	V103	V104	V105	V106	V107	V108	V109	V110	V199	V201 – V20X	V101B	V301
End of week	-2 to 0	0	12	24	36	48	60	72	84	96	108	120	128	Every 12 weeks	NA	132
Open-label Treatment Phase Completion form													х			
Follow-Up Phase Completion form																x

1 – All study visit target dates are to be calculated from the Day 1 visit date and all study procedures for a given visit should be completed on the same day.

2 – The Follow-Up Visit is required 8 weeks after last IMP injection (erenumab). The Follow-Up visit can be skipped if any other safety follow up visit occurred 4 weeks after last study visit. 3 – Including prior prophylactic medication.

4 – Includes blood pressure, pulse and temperature.

5 – SAEs will be collected after signing of the informed consent through the end of the Follow-Up Epoch end of study. Non-serious AEs will be collected starting at Baseline Visit through the end of the Follow-Up Epoch.

6 – Study drug erenumab will be dispensed to the patient at the center during the applicable study visit for home application. Last study drug application will be at week 124.

8 - Should be additionally performed at any visit if deemed necessary by the investigator due to AEs

9 Should be performed/registered by the investigator prior to dosing during DBTE.

X = Assessment to be recorded in the source documents and the clinical data base; S = Assessment to be recorded as source documentation only.

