# 9 Study discontinuation and completion

# 9.1 **Discontinuation**

## 9.1.1 **Discontinuation of study treatment**

Discontinuation of study treatment for a subject occurs when study treatment is stopped earlier than defined in the protocol and not for a planned "drug-holiday", and can be initiated by either the subject or the investigator.

The investigator must discontinue study treatment for a given subject if, he/she believes that continuation would negatively impact the subject's well-being.

Study treatment must be discontinued under the following circumstances:

- Subject/guardian decision
- Pregnancy
- Use of prohibited treatment as per recommendations in the prohibited treatment section
- Any situation in which study participation might result in a safety risk to the subject
- Any laboratory abnormalities that in the judgment of the investigator, taking into consideration the patient's overall status, prevents the patient from continuing participation in the study

If discontinuation of study treatment occurs, the investigator should make a reasonable effort to understand the primary reason for the subject's premature discontinuation of study treatment and record this information.

Subjects who discontinue study treatment or who decide they do not wish to participate in the study further should NOT be considered withdrawn from the study UNLESS they withdraw their consent (see withdraw of informed consent section,). Where possible, they should return for the assessments indicated in the assessment schedule. If they fail to return for these assessments for unknown reasons, every effort (e.g. telephone, e-mail, letter) should be made to contact the subject/pre-designated contact as specified in the lost to follow-up section. This contact should preferably be done according to the study visit schedule.

If the subject cannot or is unwilling to attend any visit(s), the site staff should maintain regular telephone contact with the subject, or with a person pre-designated by the subject. This telephone contact should preferably be done according to the study visit schedule.

After study treatment discontinuation, at a minimum, in abbreviated visits, the following data should be collected at clinic visits or via telephone/email contact:

- New / concomitant treatments
- Adverse Events/Serious Adverse Events

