2.1.1.1 Study dates

First IMP Dose Date

The first IMP dose date is the date on which a subject is administered the first dose of erenumab following screening. For subjects who are screened but no dose administration is documented, first IMP Dose Date is considered missing.

Last IMP Dose Date

The last IMP dose date for each subject is defined as the latest date of a dose administration.

Time under treatment

Time under treatment is defined as (Last IMP Dose Date + 28 – First IMP Dose Date) - Duration of treatment interruption due to drug holiday (if applicable).

Exposure-adjusted incidence rate of AE

Exposure-adjusted patient incidence rate of AE is defined as the total number of patients who reported an AE in a given time period of follow up divided by total patient-years of exposure in that period.

Total patient-years of exposure is defined as the sum of the duration of exposure from first IMP dose to the earliest of end-of-study date, end-of-OLTP date, or first report of event across all patients during the OLTP.

Study Day

Study Day 1 is defined as the first IMP dose date. For patients who are screened but not dosed after inclusion, Study Day 1 is defined as the date of screening visit.

Study Day is defined as the number of days from Study Day 1.
Before Study Day 1:
Study Day = (Date of Interest – Date of Study Day 1)

On or after Study Day 1: Study Day = (Date of Interest – Date of Study Day 1) + 1

Therefore the day prior to Study Day 1 is Day -1.

Drug holiday

Drug holiday is defined as a voluntary single treatment interruption of up to 24 weeks introduced after at least 12 weeks of treatment in the open-label Treatment Epoch.

After the "Planned date of last dose before drug holiday" starts a 28 day drug holiday initiation period, followed by the actual drug holiday period (see definitions below).

Drug holiday planned

Drug holiday is defined as planned if in the eCRF "Planned date of last dose before drug holiday" is not missing.

Drug holiday started

Drug holiday is defined as started if in the eCRF "Planned date of last dose before drug holiday" is not missing and lies at least 4 weeks before the cut-off date (regarding the interim analysis) resp. end of study date and up to day 28 after the "Planned date of last dose before drug holiday" no IMP application is documented.

Return to treatment after drug holiday

Patients are defined as returned after drug holiday if in the eCRF "Date of first dose after drug holiday" is not missing.

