
Completion of drug holiday

Patients are defined to have completed their drug holiday if they either returned after drug holiday (see below) or if they discontinued study treatment, i.e. date of first dose after drug holiday or date of discontinuation of study treatment or date of study completion/discontinuation is given.

Drug holiday initiation period

The drug holiday initiation period

is defined as the 28 days-interval after start of the drug holiday

initiation period.

Start of drug holiday initiation period

The start date of drug holiday initiation period is defined as date of "planned date of last dose before drug holiday" from the eCRF + 1.

Novartis	Confidential	Page 10 of 34
SAP v1.1		CAMG334ADE03

Start of actual drug holiday period

The start date of the actual drug holiday period is defined as date of "planned date of last dose before drug holiday" + 28.

Patient-level End of Study (EoS) Date

The end of study (EoS) date for each subject is defined as the last date on which the subject participated in the study. The date will be recorded on the Treatment / study Completion eCRF page (Date of study completion/discontinuation).

On-treatment period

The on-treatment period lasts from the date of first administration of study treatment to 84 days after the date of the last actual administration of study treatment.

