2.5.2 Statistical hypothesis, model, and method of analysis

The primary analyses will be conducted dividing the number of AEs by the time under treatment and standardizing it per 100 person-years. Exact Pearson-Clopper confidence intervals for single proportions will be calculated in order to evaluate the precision of the estimated parameter. No formal hypotheses testing will be conducted.

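### Does the time-under-treatment formula remove drug-holiday days that were never counted, for patients who do not resume dosing?

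*SAP*

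**What the plan says.** SAP 2.1.1.1 gives time under treatment as "Last IMP Dose Date + 28 – First IMP Dose Date) - Duration of treatment interruption due to drug holiday (if applicable". SAP 2.5.2 then uses it: "The primary analyses will be conducted dividing the number of AEs by the time under treatment and standardizing it per 100 person-years".

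Three other definitions in SAP 2.1.1.1 bear on the point.

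- Last dose: "The last IMP dose date for each subject is defined as the latest date of a dose administration". For a patient who never resumes, this is a dose before the holiday.
- Holiday start: "The start date of the actual drug holiday period is defined as date of" the planned last pre-holiday dose, plus 28 days. The 28 days before that form a separate initiation period.
- Holiday completion: a patient counts as having completed the holiday on return or on stopping treatment, that is, when "date of first dose after drug holiday or date of discontinuation of study treatment or date of study completion/discontinuation is given".

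The protocol leaves return optional (6.1.4): "After such a voluntary treatment interruption within the 128 weeks of the Treatment Epoch patients may return to the treatment schedule". Footnote 6 to Table 8-1 fixes the end of dosing: "Last study drug application will be at week 124". Section 9.1.1 keeps a holiday apart from stopping treatment: "Discontinuation of study treatment for a subject occurs when study treatment is stopped earlier than defined in the protocol and not for a planned" holiday. Section 4.2 describes an interruption of at most 24 weeks that ends with the patient going back on the regimen.

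No visible passage in either document states how the holiday duration in the formula is calculated.

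**The concern.** The subtraction is right for a patient who resumes, because the span from first to last dose then contains the holiday. It looks wrong for a patient who does not, because the span ends before the holiday starts.

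Such patients are foreseen. Some may stop treatment during the holiday. Others may still be on holiday when the study ends: with the last dose at week 124, an actual holiday of 24 weeks starting after week 124 - 24 = 100 leaves no scheduled dose after it, and no latest start is visible.

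The completion definition supplies an end date for both groups, so a programmer could derive a positive duration for someone who never resumed. These patients' adverse events would stay in the numerator while their person-time was cut, or turned negative. The error would run one way, towards too high a primary rate. The subgroup repeats in SAP 2.5.4 would feel each case more.

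**Working it through.** The documents give no total person-time and no expected event rate, so there is no stated figure to reproduce. The check is date arithmetic on the formula.

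**Inputs.** Counted time before subtraction, with the last dose at week w: 7w + 28 days (SAP 2.1.1.1). Longest holiday: 24 weeks = 168 days (Protocol 3). Last planned dose: week 124 (Protocol Table 8-1). Share of patients who start a holiday and never resume: not given, assumed 1% to 10%.

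**A patient who resumes.** Dosed to week 124 with a 168-day holiday: 124 × 7 + 28 = 896; 896 - 168 = 728 days. This is correct, because the 896 days contain the holiday.

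**A patient who does not resume, dosed as planned.** Counted time ends at last dose + 28. The actual holiday starts at planned last dose + 28. The intervals touch and do not overlap, so the correct subtraction is 0. If 168 days were entered instead:

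| Last dose | Correct days | With 168 subtracted |
|---|---|---|
| Week 12 | 84 + 28 = 112 | -56 |
| Week 20 | 140 + 28 = 168 | 0 |
| Week 52 | 364 + 28 = 392 | 224 (43% low) |
| Week 100 | 700 + 28 = 728 | 560 (23% low) |

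**Pooled rate.** Let g be the share who do not resume, and let everyone else contribute 896 days. The rate is inflated by

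[(1 - g) × 896 + g × (7w + 28)] / [(1 - g) × 896 + g × (7w + 28 - 168)].

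The number of patients cancels. With w = 52:

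- g = 1%: 890.96 / 889.28 = 1.0019, or 0.2% too high.
- g = 5%: 870.8 / 862.4 = 1.0097, or 1.0% too high.
- g = 10%: 845.6 / 828.8 = 1.0203, or 2.0% too high.

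Moving the last dose between weeks 12 and 100 barely matters: at 10% the range is 1.95% to 2.1%. A 12-week holiday (84 days) halves the effect: at 5%, 870.8 / 866.6 = 1.0048, or 0.5%.

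**How large a share is plausible.** Protocol 12.8.2 plans on 4.2% discontinuing for adverse events and 22.2% for other reasons, 26.4% together. A 10% share would already mean 10 / 26.4 = 38% of all discontinuations falling in a holiday, unless many patients end the study on a late one. Hence 1% to 5% is the more plausible range.

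**A yardstick.** Protocol Table 1 (12.8.1) accepts ±3.1 points at 85%, which is 3.1 / 85 = 3.6% relative. That precision is for a proportion, not a rate, so the comparison is only rough.

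**The case for a change.** The strongest case for a change is that the words in brackets read most naturally as meaning that the patient had a holiday, not that the patient came back from one. The SAP defines return to treatment separately, yet the formula does not refer to it, and the completion definition supplies an end date without a return. Two competent programmers could differ. A negative patient time is impossible on its face, the rate is the primary endpoint, and a single sentence would settle the matter. The same silence affects the exposure variant in SAP 2.1.1.4 that leaves out the holiday.

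Part of this stands: the visible text does not define the duration, and the arithmetic above is right if a positive value is entered. The rest is weaker.

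- The completion definition classifies patients; nothing says that it feeds the subtraction. The quantity is called time under treatment, and removing days outside the counted span contradicts that name. With Protocol 4.2, which runs the holiday up to resumed dosing, zero is the sensible value for a patient who does not resume.
- The public SAP is visibly cut where holiday rules could sit. The numbering jumps from 2.6 to 2.8, from 2.10 to 2.12 and from 5.5 to 5.8; section 2.14 is cited but not shown; and the drug holiday analysis set in 2.2 has no visible analysis. A rule may stand in that text.
- The full 168 days needs a patient to use the whole allowance and then never resume. A negative value also needs a last dose before day 140 (168 - 28). Someone who stops earlier in the holiday would lose only the days elapsed.
- SAP 2.1.1.1 also defines person-years up to the first event, the end of the open-label period or the end of the study, with no holiday subtraction. If that definition governs the primary rate, this point does not touch it. Which of the two applies is a separate question.

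**Conclusion.** No change is called for. No stated rule is shown to give a wrong result. The error appears only if an analyst enters a non-zero holiday duration for a patient who never resumed, which no visible text instructs and which the formula's own qualifier lets the analyst set to zero. This is missing detail of a kind that programming normally settles correctly.

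If it were handled badly, the primary rate would be about 0.2% to 1.0% too high, in relative terms, with 1% to 5% of patients not resuming after a full 24-week holiday, and about 2% too high at 10%. These figures assume that all other patients complete 128 weeks without a holiday and that the last pre-holiday dose was given as planned. The shares and holiday lengths are assumptions; the documents give only the 24-week maximum. Because the analysis is descriptive, with no hypothesis test, a shift of that size would not alter what the study concludes about long-term safety.

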2.1.1.4 Safety endpoints

Safety summaries (tables, figures) include only data from the on-treatment period with the exception of baseline data which will also be summarized where appropriate (e.g. change from baseline summaries). In addition, a separate summary for death including on treatment and post treatment deaths will be provided. In particular, summary tables for adverse events (AEs) will summarize only on-treatment events, with a start date during the on-treatment period (treatment-emergent AEs).

Discontinuation of treatment due to AE during the Treatment Epoch

Discontinuation of treatment due to AE during the Treatment Epoch is determined by the flag on the Treatment Completion eCRF page. "Death" as a reason for treatment discontinuation will be also included in AEs leading to treatment discontinuation.

Treatment-Emergent Adverse Event (TEAE)

Treatment emergent adverse events are defined as AEs occurred on or after the first dose of study treatment. AEs registered prior and after the first dose of study treatment are considered as treatment emergent if they have increased severity based on preferred term any time after the first dose of study treatment.

In case of missing data on a day of AE start date, the AE is considered as treatment emergent if *date of first dose of study treatment* \leq *latest possible start date*

Please, see section 5.1.2 AE date imputation for "latest possible start date" definition.

Serious Adverse Event (SAE)

SAEs are determined by the flag on the Adverse Events eCRF page.

Treatment-Related Adverse Event

Treatment-emergent adverse event is defined as treatment-related, if investigator considered it as having a reasonable possibility to be related to study treatment, which is reflected in the eCRF with a corresponding flag.

Adverse Event leading to dose adjustment

Adverse event is defined as leading to dose adjustment if at least one of the following actions was taken with the study treatment due to AE:

- dose increased
- dose reduced
- drug interrupted
- drug withdrawn

Novartis	Confidential	Page 12 of 34
SAP v1.1		CAMG334ADE03

Duration of exposure to IMP

For all calculations of exposure, dose date refers to receiving dose > 0. The duration of exposure to IMP is computed as min (last IMP dose date + 27, EoS date) – first IMP dose date + 1 either including the time of drug holiday or excluding the time of drug holiday.

Subject Incidence

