2.5 Analysis supporting primary objective(s)

The primary aim of the study is to evaluate the long-term safety of 70 and 140 mg erenumab in patients with episodic or chronic migraine.

Analysis on primary endpoint should be done based on the Safety Set (SAF).

2.5.1 **Primary endpoint(s)**

The primary endpoint variable is the exposure adjusted incidence rate of AEs during the openlabel treatment epoch per 100 subject years.

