2.5.3 Handling of missing values/censoring/discontinuation

Missing data will not be imputed for primary endpoints.

Novartis	Confidential	Page 17 of 34
SAP v1.1		CAMG334ADE03

For every patient, it can be determined whether he/she discontinued for AE-related reasons. Non-AE-related discontinuations or losses to follow up will not be counted as AE-related discontinuations. AE-related discontinuations are counted as events, discontinuation due to other reasons are not counted as events.

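### The primary AE rate has two incompatible formulas in the SAP, and the planned Clopper-Pearson interval suits neither of them

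*SAP*

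**What the plan says.** The endpoint is named consistently. SAP 2.5.1 states: "The primary endpoint variable is the exposure adjusted incidence rate of AEs during the openlabel treatment epoch per 100 subject years". Protocol Table 2-1 and Section 12.4.1 agree.

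**Formula A (events).** SAP 2.5.2: "The primary analyses will be conducted dividing the number of AEs by the time under treatment and standardizing it per 100 person-years". Protocol 12.4.1 has the same sentence. SAP 2.1.1.1 defines time under treatment as last dose date plus 28 days, minus first dose date, minus any drug holiday. Nothing stops the clock at an AE.

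**Formula B (patients, first event).** Directly below, under the heading *Exposure-adjusted incidence rate of AE*, SAP 2.1.1.1 reads: "Exposure-adjusted patient incidence rate of AE is defined as the total number of patients who reported an AE in a given time period", divided by patient-years in that period. Patient-years run from first dose to the earliest of the end-of-study date, the end-of-OLTP date, "or first report of event across all patients during the OLTP". Holiday time is not mentioned. SAP 2.1.1.4 defines duration of exposure "either including the time of drug holiday or excluding the time of drug holiday".

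**Interval.** SAP 2.5.2 and Protocol 12.4.1: "Exact Pearson-Clopper confidence intervals for single proportions will be calculated in order to evaluate the precision of the estimated parameter".

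**Counting rule.** For the primary endpoint, SAP 2.5.3 and Protocol 12.4.2 say: "AE-related discontinuations are counted as events, discontinuation due to other reasons are not counted as events".

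**The concern.** The study has one arm and no hypothesis test, so this rate and its interval are the whole primary result. The two formulas answer different questions. A measures AE burden per year on treatment. B measures how soon patients report any AE, and it discards all person-time after a first AE, however minor.

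A programmer who looks up the endpoint by name reaches B; one who reads the primary analysis section reaches A. With both in the SAP under one label, the choice could be made, or defended, after the data are seen.

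The surrounding text does not settle it. The counting rule in the primary section describes AE-related discontinuation, which is the secondary endpoint, and there is no rule for repeated AEs. The interval is for a proportion, so the precision of the headline figure is undefined too.

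**Working it through.** **Inputs from the documents:** 87% of patients with at least one AE over three years, and 500 patients (Protocol 12.8.1); 128 weeks of treatment (Protocol 6.1.4); last dose at week 124 (Protocol Table 8-1, note 6); holiday of up to 24 weeks.

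**Assumptions:** 95% two-sided intervals (no level is stated), no dropout and, except where stated, no holiday. AE recurrence is not given in the documents, so it is varied.

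**1. The plan's own precision figures.** Protocol Table 1 gives ±4.0, 3.5, 3.1 and 2.6 points at 70%, 80%, 85% and 90%. The normal-approximation half-width 1.96 × √(p(1−p)/500) gives 4.02, 3.51, 3.13 and 2.63, so the table reproduces. It describes the crude proportion with any AE, which is neither A nor B.

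**2. One patient.** Take three AEs, the first at day 60, and a 24-week holiday.
- A: 3 events over (124×7 + 28 − 168)/365.25 = 1.99 years.
- B: 1 event over 60/365.25 = 0.16 years.

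A full holiday cuts time under treatment from 128 to 104 weeks (24/128 = 19%).

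**3. The whole study.** T = 896/365.25 = 2.453 years, so 500 × T = 1,227 person-years (PY). A constant hazard that reproduces 87% at three years is −ln(0.13)/3 = 0.680 per year. To let AE rates vary between patients, use a gamma-Poisson model with shape k; the mean rate m solves (1 + 3m/k)^−k = 0.13. S(t) is the probability of no AE by time t.
- A = 100 × 500mT / 1,227, which equals 100m.
- B = 100 × 500(1 − S(T)) / (500 × ∫S from 0 to T).

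| Model | m per year | AEs | Patients with an AE | First-event PY | A per 100 PY | B per 100 PY | A/B |
|---|---|---|---|---|---|---|---|
| Constant hazard | 0.680 | 834 | 406 | 597 | 68 | 68 | 1.0 |
| k = 2 | 1.182 | 1,450 | 417 | 501 | 118 | 83 | 1.4 |
| k = 1 | 2.231 | 2,736 | 423 | 419 | 223 | 101 | 2.2 |
| k = 0.75 | 3.546 | 4,350 | 425 | 374 | 355 | 114 | 3.1 |

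**4. The interval under A.** There is no binomial denominator. At k = 2, 1,450 AEs exceed both 500 patients and 1,227 PY, so Clopper-Pearson cannot be computed. Where it can be forced (834 out of 1,227) it gives 65.3 to 70.6, against exact Poisson 63.5 to 72.8.

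Plain Poisson is itself too narrow when patients differ. With dispersion φ = 1 + mT/k, the half-width is 196 × √(φm/1,227):
- k = 2: φ = 2.45, half-width 9.5 rather than 6.1.
- k = 1: φ = 6.47, half-width 21.3 rather than 8.4.

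**5. The interval under B.** Suppose 425 of 500 (85%) have an AE at a constant hazard: 550 first-event PY and a rate of 77.3. Clopper-Pearson for the proportion is 81.6% to 88.0%, which is not on the rate scale. Applying those limits to the patient count and dividing by the same person-time gives 74.2 to 80.1, against exact Poisson 70.2 to 85.0. Transforming the limits by −ln(1−p)/T gives 68.9 to 86.5. That is close, but it needs equal follow-up and a constant hazard, and the plan does not state this step.

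**The case against.** The strongest reply is that the governing formula is set. Protocol 12.4.1 and SAP 2.5.2 give A in identical words; in the available text, time under treatment serves only that analysis; and SAP Section 4 declares no change of primary formula. B speaks of a *patient* incidence rate and sits in a general list of definitions. Some SAP sections and the table shells are not available, so B may have a use elsewhere. On this reading a rename is enough.

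This has weight: using B as primary would contradict both primary-analysis sections. It does not remove the defect. B stands under the endpoint's name, the supplementary analyses for the primary endpoint (SAP 2.5.5) are marked not applicable, and the AE summaries in SAP 2.8.1 are numbers and percentages, not rates. The interval error also stands if A is accepted outright.

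Other replies hold in part:
- B can be read as not subtracting the holiday, since it sets its own start and stop. That is the plain reading, but SAP 2.1.1.4 leaves both versions of exposure open.
- Number of AEs, on its face, counts every event, and treatment-emergent status is defined. How recurrences of one AE are counted is still not stated. The SAP also takes AEs up to 84 days after the last dose into its summaries, while time under treatment ends at 28 days.
- The discontinuation text is misplaced wording and alters neither formula. It does occupy the place where the counting rule should be.
- The ratios 1.0 to 3.1 are not bounds. With one AE per patient on average and 85% affected, A is 500/1,227 = 40.8 and B is 77.3, so the direction can reverse.
- The choice among rate intervals is partly preference. That a binomial interval is wrong for a rate is not.

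**Conclusion.** The concern holds and should be fixed before the analysis. The primary label covers two quantities that can differ severalfold, and the planned interval is valid for neither. The operative text leans to the event-based formula, but the SAP does not settle the matter.

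The 87%, the 500 patients and the 128 weeks are the plan's; the recurrence pattern, full follow-up and 95% level are assumptions. Under the gamma-Poisson range the two rates agree only if all patients share one constant hazard, and they separate as patients differ more. The formula conflict and the unsuitable interval follow from the text and do not depend on those assumptions.

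**What to change.** - **One primary formula.** State it identically in SAP 2.1.1.1, SAP 2.5.2 and Protocol 12.4.1. The smallest change keeps the event-based rate as primary and renames the SAP 2.1.1.1 quantity *first-event patient incidence rate*, as a supplementary analysis, stating whether holiday time counts in its denominator.
- **Counting rule.** Replace the discontinuation text in SAP 2.5.3 and Protocol 12.4.2 with the rule for the chosen rate: which AEs count, including those with onset in a drug holiday or after the last dose; how repeats of the same AE count; and when follow-up ends.
- **Interval.** Use a patient-clustered (robust) or negative binomial interval for the event rate, and exact Poisson for the first-event rate. Keep Clopper-Pearson for crude proportions. State the confidence level.
- **Precision.** Restate the planned precision for the chosen rate, since Protocol Table 1 covers only the proportion with any AE.
- **Record.** Note any departure from the protocol in SAP Section 4.

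The cost is SAP wording, a matching protocol clarification and one extra table. No new data are needed.

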### 4 **Rationale**

#### 4.1 **Rationale for study design**

Until now long-term safety and tolerability data of erenumab in a large group of patients are still limited. This 128-week open-label study will provide further treatment to patients still blinded for the randomization of the study CAMG334ADE01 (Eudract number:2019 -

Novartis	Confidential	Page 19
Clinical trial protocol V01	Protocol No. CAMG334ADE03	-

002201 - 22) and will provide data about the long-term safety and tolerability of Erenumab and patients' quality of life during long-term treatment. The regular assessments in a controlled trial allows a close observation of safety parameters during long-term treatment with erenumab. Furthermore, while regular reviews of treatment outcome and drug holidays are routine in migraine prophylaxis and also recommended in the German S1 guideline (DGN 2018), there are no data regarding erenumab treatment yet. Besides options to adjust the dose, an optional drug holiday is therefore included in this open-label study and the effects of a treatment interruption on safety, tolerability, efficacy and quality of life will be investigated.

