#### 12.5.2 Safety endpoints

For all safety analyses, the safety set will be used. All listings and tables will be presented.

Safety summaries (tables, figures) include only data from the on-treatment period with the exception of baseline data which will also be summarized where appropriate (e.g. change from baseline summaries). In addition, a separate summary for death including on treatment and post treatment deaths will be provided. In particular, summary tables for adverse events (AEs) will summarize only on-treatment events, with a start date during the on-treatment period (treatment-emergent AEs).

The on-treatment period lasts from the date of first administration of study treatment to 112 days after the date of the last actual administration of study treatment.

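### The on-treatment period hangs on the last dose ever given, so a late drug-holiday AE enters the summary tables only if the patient later restarts

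*SAP*

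**What the plan says.** SAP 2.1.1.1 gives each patient one continuous on-treatment period, "from the date of first administration of study treatment to 84 days after the date of the last actual administration of study treatment". The anchor is the final dose: "The last IMP dose date for each subject is defined as the latest date of a dose administration". Protocol 12.5.2 sets the end at "112 days after the date of the last actual administration of study treatment", and SAP section 4 does not list the shorter window as a change.

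SAP 2.1.1.4 then applies the period as a filter: "Safety summaries (tables, figures) include only data from the on-treatment period", with baseline data excepted. It says specifically that AE tables keep only events that begin inside the period. The same section also defines treatment-emergent AEs as those from the first dose onwards, with no end date, and SAP 2.8.1 repeats that open-ended wording.

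On the holiday, SAP 2.1.1.1 says: "Drug holiday is defined as a voluntary single treatment interruption of up to 24 weeks introduced after at least 12 weeks of treatment". It places the start of the actual holiday 28 days after the planned last dose, and it recognises that a holiday can end in treatment discontinuation instead of a restart. Protocol 4.1 states that "the effects of a treatment interruption on safety, tolerability, efficacy and quality of life will be investigated".

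**The concern.** The period has no break for the holiday. If the patient restarts, the last administration lies after the holiday and the whole off-drug stretch becomes on-treatment. If the patient does not restart, the last administration is the last pre-holiday dose and the period closes during a long holiday. Inclusion of an event is thus settled by something that happens afterwards and that the event may itself bring about, which is selection on a future outcome.

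Two things are at stake. A late-holiday AE that deters a patient from resuming is left out of the SOC/PT, severity and SAE tables, while the same event in a patient who resumes is counted. And the returners' off-drug events are mixed into tables labelled on-treatment. The same filter reaches other safety summaries, such as vital signs at late holiday visits.

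**Working it through.** **Plan figures.** The plan gives no figure for this point. Its only precision figures for the AE endpoint (protocol 12.8.1, Table 1, n = 500) reproduce as 1.96 × √(p(1−p)/500) = 4.02, 3.51, 3.13 and 2.63% for p = 70, 80, 85 and 90%, against the stated 4.0, 3.5, 3.1 and 2.6%. Nothing below depends on them.

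**Inputs**
- Window W: 84 days (SAP 2.1.1.1) or 112 days (protocol 12.5.2).
- Longest holiday: 24 × 7 = 168 days (SAP 2.1.1.1).
- Gap G from last pre-holiday dose to end of holiday: 168 days if the 24 weeks run from the last dose, or 168 + 28 = 196 days if they run from the SAP's start of the actual holiday. Planned and actual last pre-holiday dose are taken to coincide.

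**Uncovered days.** For a patient who does not restart, U = G − W. For one who restarts, U = 0, because the period runs to at least the restart date + W.

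| 24 weeks counted from | G | U, W = 84 | U, W = 112 |
|---|---|---|---|
| last dose | 168 | 84 (50%) | 56 (33%) |
| last dose + 28 days | 196 | 112 (57%) | 84 (43%) |

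The longer window shortens the uncovered stretch but does not remove it.

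**Same event, two patients.** Both have the same last pre-holiday dose and an SAE starting 120 days later. One restarts, so the SAE lies inside the period and is tabulated. The other does not. That patient's period closed on day 84 (or day 112), so the SAE is not tabulated.

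**Who is unaffected.** For a patient who completes treatment, the last dose is at week 124 (protocol Table 8-1 footnotes). The period ends at 124 + 84/7 = week 136, after the week 132 follow-up visit. An AE starting within W days of the last pre-holiday dose is also kept, whatever happens later.

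**Illustration only.** Take 100 patients with a full holiday, all observed to its end, and assume r = 0.5 to 2 AEs per patient-year (not in the documents). AEs starting in the late stretch = 100 × r × U/365.25:
- U = 56: 7.7 to 30.7
- U = 84: 11.5 to 46.0
- U = 112: 15.3 to 61.3

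If a share q of these falls in non-returners, q × that number is left out. With q assumed at 10% to 50%, this is 0.8 to 15.3, 1.1 to 23.0 and 1.5 to 30.7 AEs per 100 holiday patients. For a type of event that always prevents a restart, q is 100%.

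**The case against.** **The treatment-emergent definition has no end date.** Under that wording alone, in SAP 2.1.1.4 and 2.8.1, the late event would be tabulated for both patients. This stands as a conflict in the SAP. But the filter sentence in 2.1.1.4 expressly limits the AE tables to the on-treatment period, so it is the more natural governing rule. At best, two programmers could build different tables.

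**Other outputs keep these events.** This stands. A reader might infer that only deaths are protected, but SAP 2.8.1 lists all AEs and SAEs, and discontinuation due to AE comes from an eCRF flag, not from the window. The remaining oddity is that a patient could count as discontinued for an AE that is missing from the AE tables.

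**The data may be incomplete.** This stands in part. Protocol Table 8-1 marks AEs and SAEs at the 12-weekly holiday visits. After treatment discontinuation, protocol 9.1.1 asks for the scheduled assessments only where possible, 10.1.1 requires AE monitoring for at least eight weeks after the last dose, and routine SAE reporting under 10.1.3 ends eight weeks after the last injection. Late events in non-returners will not all be captured.

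**A holiday analysis may already exist.** This cannot be excluded. The SAP defines a Drug Holiday Analysis Set, and its interim analysis section is not visible in the public text. A reader might infer that the protocol's question on interruption and safety goes unanswered, but the documents do not show that.

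**Late-holiday events are off-drug anyway.** Then the returners' events do not belong in the on-treatment tables either. The defect is the unequal rule.

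**Conclusion.** The point holds for the summary tables. For a full 24-week holiday, 84 to 112 days are uncovered under the SAP window, or 56 to 84 under the protocol window, for a patient who does not restart, and none for one who does. This arithmetic rests only on the documents' definitions and on the filter sentence governing the tables. The effect on event counts is unknown: holiday uptake, non-return and AE rates are not given, and the illustration shows only how the result moves with them.

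Two stronger readings are not supported:
- A reader might infer that the AE rate is halved: if an AE cut the chance of restarting from 80% to 40%, 0.40/0.80 = 0.5. The affected tables report numbers and percentages of subjects, not rates. Counted person-time would also fall. At an assumed 1 to 2 AEs per patient-year over 112 days (Poisson), 26% to 46% of patients have an event, counted person-time is about 69% to 62%, and the ratio is 0.58 to 0.65.
- A reader might extend the point to the summary of exposure duration. That has its own anchor (last dose + 27 days) and can also be given excluding the holiday, so the on-treatment definition does not govern it.

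**What to change.** 1. In SAP 2.1.1.1, define on-treatment dose by dose: an event or assessment is on-treatment if it starts within W days after the most recent actual administration. Apply this to the last pre-holiday dose whether or not the patient restarts.
2. Use one W, reconciled between protocol 12.5.2 and the SAP, and record any change in SAP section 4.
3. Align the treatment-emergent wording in SAP 2.1.1.4 and 2.8.1 with that period.
4. Show later holiday AEs and SAEs in one separate off-treatment table, with off-drug person-time, for all patients who started a holiday, returners and non-returners alike. Skip this if the unshown holiday analyses already provide it.

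The cost is one definition, its matching wording, one programmed flag and possibly one table; no new data are needed. Some returners' holiday AEs move from the main tables to the holiday table. The change makes the main tables consistent; it does not bring non-returners' late events back into them.
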